## **Arms and Interventions**

Arms	Assigned Interventions	
Experimental: EXO-1 Participants (n=10) in this group will receive standard therapy and exosomes of the first type.	Procedure/Surgery: EXO 1 inhalation Twice a day during 10 days inhalation of 3 ml special solution contained 0.5-2x10^10 of nanoparticles (exosomes) of the first type.	
Experimental: EXO-2 Participants (n=10) in this group will receive standard therapy and exosomes of the second type.	Procedure/Surgery: EXO 2 inhalation Twice a day during 10 days inhalation of 3 ml special solution contained 0.5-2x10^10 of nanoparticles (exosomes) of the second type.	
Placebo Comparator: Placebo Participants (n=10) in this group will receive standard therapy and inhalation placebo solution.	Procedure/Surgery: Placebo inhalation Twice a day during 10 days inhalation of 3 ml special solution free of nanoparticles (exosomes).	

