## **Eligibility**

Minimum Age: 18 Years

Maximum 65 Years

Age:

Sex: All

Gender No

Based:

Accepts No Healthy

Volunteers:

Criteria: Inclusion Criteria:

- Ability to understand the study objectives and risks and provide signed and dated informed consent;
- Confirmed COVID-19 infection (by PCR or antibody test);
- Pneumonia requiring hospitalization, and oxygen saturation of <94% indoors or a need for auxiliary oxygen. The confirmed volume of lung damage by CT: not less than 30% and not more than 80%;
- · ability to proceed with inhalation by self;

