#### Research methods and STATISTICAL CONSIDERATIONS

Title	Purpose	Method	Frequency	Statistics
Number of	Safety	Collection of	After each	Numeric data, calculated
participants with minor and serious side effects	assessment of the procedure.	information about unwanted reactions to inhalation, for example, 1) temperature increase, 2) allergic reaction in the form of swelling Quincke, rash, seizures, etc.; 3) bronchospasm for inhalation	procedure	as a percent from whole patients in the group.
Biochemistry of blood	Evaluation of procedure efficiency	C-reactive protein, LDH	At the beginning of inhalation (day 1) and on next day of last inhalation (day 11)	The difference in each group between baseline and day 11 will be measured by T-test. The data will be presented as a Mean with full range (minmax). The difference will be calculated as Mean

				difference with Standard Deviation (SD)
Time to Clinical Recovery (TTCR)	Evaluation of procedure efficiency	Calculation of days in hospital	Once at the end of trial	The data will be presented as a Mean with Standard Deviation (SD)
SpO2 Concentration Changes	Evaluation of procedure efficiency	The concentration of SpO2 by Pulse oximetry device during procedures and compared to placebo.	Before and after each inhalation (total 4 measures per day). 10 days.	The intraday data (4 measures per day) will be calculated as a Median by day. The Median by day data (10 measures) will be processed by T-test intragroup and between groups. The data in tables will be presented as a Median (Me) with 25-75 quartile range.

The results will be statistically processed using parametric and non-parametric statistics methods using STATA version 9.0, Statistica for Windows version 6.0 and MS Office Excel 2007. Changes from the start of therapy and after will be compared using the T-test, comparing data between the main group and the control group using non-parametric method box-plot (data are presented in Me - median format with an indication of 25% (q1) and 75% (q3) quartile.

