## STATISTICAL CONSIDERATIONS

This study will enroll patients with PCR confirmed COVID according inclusion criteria.

The trial has three groups, each with 10 subjects (n=30). All eligible study subjects will be randomized, double-blinded, to either the two treatment groups or placebo group. Two main groups will be provided with exosomes in a specially provided solution, the third group (control) will receive the same solution without exosomes. Due to exosomes are nanoparticles and requires special methods and devices to be detected the hospital staff and patients have no way to check which group receives exosomes.

This is interventional, prospective, randomized double-blinded with a control group study.

The primary outcomes will be assessed at discharge of the clinic and 1 month after. Duration of study participation will be 1 months from the time of discharge from the clinic.

It is estimated that up to 2-3 research participants will be enrolled each week and that approximately 4 weeks of accrual will be necessary to enroll 10 participants.

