#### **Demographics and Baseline Characteristics**

Demographics and baseline characteristics will be summarized for all research participants. Characteristics to be examined include age, sex. The results will be statistically processed using parametric and non-parametric statistics methods using STATA version 9.0, Statistica for Windows version 6.0 and MS Office Excel 2007. Changes from the start of therapy and after will be compared using the T-test, comparing data between the main group and the control group using non-parametric method, box-plot.

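### Raw SpO2 is tested as an efficacy outcome in patients who may or may not be on oxygen, and the plan neither records nor adjusts for oxygen support

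*Combined protocol and SAP*

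**What the plan says.** The Eligibility section of the combined protocol and SAP requires pneumonia needing hospital care, with "oxygen saturation of <94% indoors or a need for auxiliary oxygen". These are two alternative routes into the trial.

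The SpO2 row of the table in Research methods and STATISTICAL CONSIDERATIONS gives the purpose as evaluating efficacy and the method as "The concentration of SpO2 by Pulse oximetry device during procedures and compared to placebo". The schedule is "Before and after each inhalation (total 4 measures per day). 10 days". The four readings of a day are reduced to their median, and "The Median by day data (10 measures) will be processed by T-test intragroup and between groups".

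Oxygen support does not appear elsewhere as a recorded item:
- Arms and Interventions gives every arm standard therapy, without defining it. Placebo patients, for example, "will receive standard therapy and inhalation placebo solution".
- Demographics and Baseline Characteristics states "Characteristics to be examined include age, sex" and names nothing else.
- Time to clinical recovery is obtained by "Calculation of days in hospital", which does not capture weaning.
- CRP and LDH are measured on days 1 and 11.

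**The concern.** A pulse oximeter reading has a different meaning with and without oxygen. The entry criterion allows both kinds of patient, and the planned analysis puts their readings on one scale. This affects day 1, before any treatment effect. Suppose one patient reads 92% without oxygen and a sicker one reads 96% with it (assumed values). Raw SpO2 ranks the sicker patient as better.

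After randomisation, oxygen support may itself respond to the patient's state. If it does, a recovering patient who is weaned and a worsening patient who is given more oxygen can both show little change in SpO2. Blinding does not remove this, because the adjustment follows saturation and not knowledge of the arm.

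At stake is the most frequently measured efficacy outcome, with up to 4 × 10 = 40 readings per patient. A real difference between exosomes and placebo could be understated on it, and the data needed to detect or correct that would not have been collected.

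**Working it through.** The plan states no effect size, SD, alpha or power for SpO2, so there is no figure of its own to reproduce. The gap is established by reading; its possible size can only be illustrated.

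**1. The gap.** The sections listed above contain every baseline and outcome item in the documents. None records flow, device, FiO2 or room-air status, standardises oxygen at the time of a reading, or adjusts for it. The SpO2 row is complete and legible, so this is not a redaction.

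**2. Two patients (all FiO2 and SpO2 values assumed).**
- A is weaned from FiO2 0.40 to room air (0.21) with SpO2 95% throughout. SpO2 change is 0; SpO2/FiO2 goes from 95/0.40 = 238 to 95/0.21 = 452.
- B is escalated from FiO2 0.32 to 0.60 with SpO2 94% throughout. SpO2 change is 0; SpO2/FiO2 goes from 94/0.32 = 294 to 94/0.60 = 157.

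Raw SpO2 scores both as unchanged. SpO2 is held constant here by construction, so this shows the mechanism and not its typical strength.

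**3. Effect on a between-arm difference.** Let L be the saturation a patient would have without support, normal with SD 3 and mean 93 (treated) or 89 (placebo). Below 94, the entry threshold used only as a reference point, oxygen corrects a fraction k of the shortfall. Means, SD and k are all assumptions.

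Expected observed value = mean + k × S, where S = SD × [zΦ(z) + φ(z)] and z = (94 − mean)/SD.
- Treated: z = 0.333, S = 3 × (0.333 × 0.631 + 0.377) = 1.76.
- Placebo: z = 1.667, S = 3 × (1.667 × 0.952 + 0.099) = 5.06.
- Observed difference = 4 − k × (5.06 − 1.76) = 4 − 3.30k, which is 2.35, 1.36 and 0.70 at k = 0.5, 0.8 and 1.

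A simulation of 20,000 trials agrees (10 per arm, saturation capped at 100, measurement noise SD 1, two-sided alpha of 0.05 assumed). Each cell gives the observed difference in points and the power:

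| Means, SD | k = 0 | k = 0.5 | k = 0.8 | k = 1 |
|---|---|---|---|---|
| 93 v 89, SD 3 | 3.99, 77% | 2.34, 67% | 1.35, 43% | 0.69, 15% |
| 93 v 89, SD 4 | 3.90, 54% | 2.39, 49% | 1.47, 36% | 0.86, 17% |
| 95 v 91, SD 3 | 3.91, 77% | 2.68, 71% | 1.93, 58% | 1.44, 41% |
| 95 v 91, SD 4 | 3.77, 54% | 2.59, 50% | 1.86, 43% | 1.38, 31% |

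In the first row, 63% of treated and 95% of placebo patients fall below 94. Much of the between-arm signal has moved into who needs support, which the plan does not record.

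**4. Room for attenuation.** With 10 per arm, a two-sample t-test at the same assumed alpha has 80% power only for a standardised difference of about 1.32.

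**5. Chance imbalance.** If half of patients enter on oxygen (assumed), the numbers on oxygen in two arms are independent Binomial(10, 0.5). The chance that they differ by 3 or more is 2 × P(Binomial(20, 0.5) ≥ 13) = 2 × 0.132 = 26%. Such an imbalance can push the comparison in either direction.

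**The case against.** Several points on the other side stand.

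- **Entry without oxygen is possible.** The criterion is either/or, so it would be wrong to say that patients are enrolled because they need oxygen. A mixed population does, however, make unadjusted SpO2 harder to read.
- **Titration is not documented.** No section says that oxygen is adjusted to saturation. That is a plausible assumption, and the argument about attenuation depends on it. The baseline mixing of readings does not.
- **The loss may be moderate.** At k = 0.5 in the first scenario, power falls only from 77% to 67%. The collapse to 15% needs complete correction of every shortfall.
- **SpO2 is not named as primary, nor is it the only repeated efficacy measure.** The second STATISTICAL CONSIDERATIONS section places primary outcomes at discharge and one month later. CRP and LDH are also repeated, and days in hospital is a further efficacy outcome.
- **Charts may hold the oxygen data.** They may, but the plan neither collects nor uses them.

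A reader might infer that uneven oxygen use would reverse the sign of the effect. The documents do not support that. Every scenario above shows the average difference shrinking, never reversing. Chance imbalance adds error in both directions, as it does for any prognostic factor in arms of 10 under blinded randomisation.

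It could also be said that SpO2 is there to show the immediate response to inhalation. The planned daily median pools the before and after readings, so that contrast is not what is analysed.

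**Conclusion.** The concern holds in a limited form. It is a matter of record that the plan tests raw SpO2 for efficacy in patients who may be on or off oxygen, and that it neither records nor adjusts for oxygen support. If oxygen follows saturation, the likely direction is towards no difference.

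The size is unknown. Under the first assumed scenario, a 4-point underlying difference appears as roughly 2.3, 1.35 or 0.7 points, depending on how much of the shortfall oxygen corrects.

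Two stronger readings go too far: that SpO2 mainly measures how well oxygen was adjusted, and that the trial's efficacy aim therefore cannot be answered. The first needs a value of k that the documents do not give. The second overlooks CRP, LDH and days in hospital. The point should be fixed, but it weakens one non-primary outcome and does not invalidate the study.

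**What to change.** In the SpO2 row of Research methods and STATISTICAL CONSIDERATIONS:

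1. Record the oxygen device and flow, or room air, with each SpO2 reading. Study Design lists the enrolment of 30 as actual, so readings may already be complete. In that case, retrieve this information from hospital charts before unblinding.
2. Analyse a measure that incorporates oxygen support, such as SpO2/FiO2, alongside raw SpO2. Fix the flow-to-FiO2 conversion before unblinding.
3. Report the number of patients on oxygen per arm per day.
4. Where oxygen data cannot be retrieved, label raw SpO2 as descriptive.

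Collected prospectively, this costs one added entry at readings already taken. Chart retrieval takes more work, for up to 40 readings per patient, and may be incomplete. FiO2 derived from nasal flow is approximate. SpO2/FiO2 also still depends partly on how oxygen is given: with assumed values, a patient reading 95% on room air scores 452, but the same patient left on 0.28 and reading 97% scores 97/0.28 = 346. That is why raw SpO2 and the counts on oxygen should be shown beside it. Nothing here changes how oxygen is given.

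### Merging before- and after-inhalation SpO2 into one daily median can hide or halve a fall after dosing, mixes short-lived with lasting effects, and leaves no pre-treatment value among the ten analysed

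*Combined protocol and SAP*

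**What the plan says.** The Arms and Interventions section gives every arm, placebo included, the same schedule: "Twice a day during 10 days inhalation of 3 ml special solution". The SpO2 row of the Research methods and STATISTICAL CONSIDERATIONS table sets the readings at "Before and after each inhalation (total 4 measures per day). 10 days" and describes the measure as "The concentration of SpO2 by Pulse oximetry device during procedures and compared to placebo". Its listed purpose is efficacy.

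The statistics column then combines the readings: "The intraday data (4 measures per day) will be calculated as a Median by day". The next step is "The Median by day data (10 measures) will be processed by T-test intragroup and between groups". The text below the table adds "Changes from the start of therapy and after will be compared using the T-test", without saying which SpO2 value marks the start of therapy.

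The plan contains no after-minus-before difference, no daily minimum, no count of falls, and no analysis of the before-inhalation readings alone. The side-effects row of the same table collects unwanted reactions after each procedure and names "bronchospasm for inhalation" among its examples, but sets no SpO2 criterion. The Eligibility section uses "oxygen saturation of <94% indoors or a need for auxiliary oxygen" to select patients and does not name it as an analysis baseline.

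**The concern.** The two kinds of reading answer different questions. A reading before an inhalation reflects the state of the lungs at that time. The change from before to after reflects how the patient tolerated that aerosol. The schedule collects them in pairs, and the daily median takes the pairs apart.

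Three things follow. First, the aim of this Phase 1/2 trial includes safety, and the patients have low saturation or need oxygen at entry. A fall after dosing that causes no symptoms would appear in none of the planned summaries. Second, a daily median can move because of a short-lived effect of the procedure, because of lasting change in oxygenation, or both, and the reader cannot tell which. Third, the within-group test is meant to show change from the start of therapy, but the first of the ten values is already mostly a treated value.

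**Working it through.** **Inputs from the documents.** Two inhalations a day for 10 days (Arms and Interventions); a reading before and after each, one median per day, and t-tests on the medians (SpO2 row). The documents give no SpO2 variability and no expected falls, so all levels, falls and SDs below are assumptions. The noise-free results do not depend on the assumed level.

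**The plan's own counts.** 2 inhalations × 2 readings = 4 readings per day. Over 10 days that is 4 × 10 = 40 readings per patient, reduced to 10 medians. This agrees with the table.

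**1. Falls after dosing.** The median of four values is the mean of the two middle ones.
- Fall after one inhalation: 94, 94, 94, 86 gives (94 + 94)/2 = 94. The 8-point fall does not show. With readings 92, 92 − d, 92, 92, the median is 92 for every d tried from 1 to 8.
- Fall after both inhalations: 94, 94, 86, 86 gives (94 + 86)/2 = 90. The 8-point fall shows as 4. In general the median is 92 − d/2 for readings 92, 92 − d, 92, 92 − d. It cannot be told apart from a level lower by d/2 all day.
- With reading noise (simulation, 400,000 draws, reading SD 1 to 2 points), a 6-point fall after one inhalation moves the median by 0.42 to 0.82 points on average. After both inhalations it moves it by 3.0.
- In the paired differences, a 6-point fall after both inhalations shows as 6.0. A 6-point fall after one shows in full in that pair, and as 3.0 in the mean of the two pairs.

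**2. Mixing of transient and lasting effects.** Suppose the before-inhalation level truly rises by 3 points, from 92 to 95, between day 1 and day 10, and a transient t follows each inhalation on the days shown.

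| Transient, day 1 | Transient, day 10 | Day-1 median | Day-10 median | Change in medians |
|---|---|---|---|---|
| +2 | +2 | 93 | 96 | 3 |
| +2 | 0 | 93 | 95 | 2 |
| 0 | +2 | 92 | 96 | 4 |
| −4 | 0 | 90 | 95 | 5 |

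A constant transient cancels from the within-group change; one that varies over days does not. Between arms, median(x, x, x + 2, x + 2) = x + 1. A +2 transient in one arm only therefore gives a 1-point difference in daily medians. The same transient in every arm gives 0.

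**3. The day-1 value.** Three of the four day-1 readings (75%) come after the first inhalation. Only one reading is untreated, so at least one of the two middle values is always post-dose, and the day-1 median is never a pure pre-treatment value. If saturation steps up by g after the first inhalation and stays there, the readings 92, 92 + g, 92 + g, 92 + g give a median of 92 + g. With a total gain of 4 by day 10 and g = 2, the change is 96 − 92 = 4 from the pre-dose reading, but 96 − 94 = 2 from the day-1 median.

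**4. Noise cost of using before-inhalation readings.** Assume independent normal reading errors with variance s². The variance of a median of four is about 0.298 s².
- Day-10 median minus day-1 median: 2 × 0.298 s² ≈ 0.6 s².
- Mean of two before-inhalation readings on day 10 minus one pre-dose reading: s²/2 + s² = 1.5 s².
- Ratio: 1.5/0.6 = 2.5.

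**The case against.** The strongest case for the plan has four parts.

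- **Other safety capture exists.** The side-effects row is open-ended, applies after each procedure, and lists fever as well as bronchospasm. A symptomatic desaturation could be recorded there. A reader might infer that the trial discards its only objective measure of tolerance. The documents do not support that: temperature is also objective, and the saturation readings are kept. What stands is narrower: no SpO2 fall is summarised anywhere, so a silent one could be missed.
- **Placebo controls for the vehicle.** Study Design gives the control arm the same solution without exosomes. A reader might infer that a brief effect of nebulising creates a false difference between arms. It does not, because an effect common to all arms cancels. A transient found in one exosome arm only would be a real effect, misread as lasting. The mixing matters for effects that differ by arm or change over the days.
- **The randomised comparison keeps early effects.** The day-1 problem touches only the within-group change, and only if the day-1 median is the starting value. The plan does not say that it is. That is a natural reading, not a stated rule.
- **The median is less noisy.** This stands. A single baseline reading costs precision with 10 patients per arm, and it comes from one time of day while later days average two. It is a reason to keep the median and add to it.

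**Conclusion.** The concern holds in this limited form. The planned summary can hide a fall after one of the day's inhalations and halves a fall after both. It mixes arm-specific or time-varying transients with lasting change in oxygenation. It also leaves no pre-treatment value among the ten that are analysed.

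It would be too strong to say that every fall is erased, since a repeatable fall after both inhalations still shows at half size. It would also be too strong to say that the trial lacks a baseline: the reading before the first inhalation is taken, but it enters the analysis only as one of four in the day-1 median.

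The halving and the 3-in-4 count follow from the schedule and the definition of a median. The point sizes are illustrations on assumed readings, and the variance figures assume independent normal errors. This is worth correcting because the safety answer improves without any new measurement, but it does not invalidate the between-group comparison of daily medians.

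**What to change.** Keep the planned daily median and add two summaries from readings already taken.

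1. **Tolerance.** For each inhalation, calculate the after-minus-before change in SpO2 and summarise it by arm. Report the number of patients per arm with any fall beyond a margin that the sponsor fixes before unblinding. The documents offer no basis for a particular value. The margin is for reporting only and is not a treatment rule.
2. **Efficacy.** Summarise the before-inhalation readings alone (mean of the two per day), with the reading before the first inhalation on day 1 named as the baseline.

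The cost is SAP wording and a little more analysis. Summary 2 is noisier: the reading-error variance of the change is about 1.5 against 0.6 times that of a single reading, which is why it should stand beside the median and not replace it. Study Design gives the enrolment of 30 as an actual count, so both additions should be declared as a late change to the plan, with the date and the blinding status at that time.

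### The SpO2 analysis sends ten daily medians per patient to a t-test without reducing them to one value per patient, and sets neither an error rate nor whether the two exosome arms are tested separately

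*Combined protocol and SAP*

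**What the plan says.** All references are to the combined protocol and SAP.

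- **Readings.** The SpO2 row of the table in *Research methods and STATISTICAL CONSIDERATIONS* schedules readings as follows: "Before and after each inhalation (total 4 measures per day). 10 days". The four readings of a day are reduced to their median.
- **Test.** The same row continues: "The Median by day data (10 measures) will be processed by T-test intragroup and between groups". Its Method cell names placebo as the comparator.
- **General text under the table.** Change from before to after treatment is to be tested with a t-test; the day that counts as after is not given. Between groups, the method is "comparing data between the main group and the control group using non-parametric method box-plot", followed by a parenthesis about presenting medians and quartiles. *Demographics and Baseline Characteristics* repeats it: "comparing data between the main group and the control group using non-parametric method, box-plot".
- **Arms.** The general text speaks of one main group. *STATISTICAL CONSIDERATIONS* has two: "Two main groups will be provided with exosomes in a specially provided solution".
- **Other outcomes.** For CRP and LDH the table gives a within-group test: "The difference in each group between baseline and day 11 will be measured by T-test". Days in hospital get only a mean and SD. SpO2 is therefore the only row that names a between-group test.
- **Not stated anywhere.** Alpha, sidedness, a repeated-measures model, a multiplicity rule, or a label marking the SpO2 analysis as exploratory.

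**The concern.** A t-test needs one independent value per patient, and the row supplies ten. Its wording allows at least three analyses: a separate test on each day, one test on all patient-days, or one test on a per-patient summary. The first two are natural readings and lead to false-positive rates well above 5%. The third does not, but the plan does not choose it.

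The contrasts are only partly fixed. Placebo is the comparator, but EXO-1 and EXO-2 could be tested separately or pooled. The general text does not settle this. It speaks of a single main group, and it assigns the between-group comparison to a non-parametric method without naming a test, whereas the row assigns it to a t-test.

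With 10 patients per arm and one outcome carrying the only named between-group test, a chance difference in SpO2 could easily be reported as evidence of efficacy. The choice among the readings could also be made after the data are seen.

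**Working it through.** **1. Counts in the plan.** 2 inhalations × 2 readings = 4 readings a day. Over 10 days this gives 10 daily medians per patient, and 10 patients × 10 days = 100 patient-days per arm. These agree with the plan. The plan states no alpha, power or effect size, so there is no inferential figure to reproduce.

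**2. Assumptions (not in the documents).** Two-sided 5% per test, no true effect, normal data, 10 patients per arm, complete readings. Within-patient correlation ρ between days is 0.3 to 0.9, either exchangeable or AR(1). Rates come from simulated null trials, at least 10,000 per scenario; repeat runs agree to about one percentage point.

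**3. Any of ten daily tests.** If days were independent, the rate would be 1 − 0.95^10 = 0.401. Correlation lowers it, as the table shows.

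**4. Pooled patient-days (100 against 100).** With exchangeable correlation, the variance of an arm mean is larger than the t-test assumes by the factor D = 1 + 9ρ. The approximate false-positive rate is 2 × [1 − Φ(1.96/√D)]:

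- ρ = 0.3: D = 3.7, 1.96/1.924 = 1.019, rate about 31%
- ρ = 0.9: D = 9.1, 1.96/3.017 = 0.650, rate about 52%

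The simulated rates are slightly higher. At ρ = 0 the pooled test holds about 5%.

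False-positive rate per exosome-placebo comparison (simulated, approximate):

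| Correlation | Any of ten daily tests | Pooled patient-days |
|---|---|---|
| Exchangeable 0.3 | 36% | 32% |
| Exchangeable 0.5 | 30% | 41% |
| Exchangeable 0.7 | 22% | 48% |
| Exchangeable 0.9 | 13% | 54% |
| AR(1) 0.3 | 39% | 14% |
| AR(1) 0.5 | 36% | 23% |
| AR(1) 0.7 | 31% | 34% |
| AR(1) 0.9 | 19% | 49% |

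**5. One value per patient.** A single t-test on a per-patient mean gives about 5% at every correlation tried. Two exosome-placebo comparisons, unadjusted, give about 9% for either arm (1 − 0.95² = 0.0975 if independent; they share the placebo arm). At 0.025 each, the either-arm rate is 4.3% to 5.0%.

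**6. Cost in detectable difference.** With 10 per arm and 80% power, a two-sample t-test detects 1.32 SD at 0.05 and 1.48 SD at 0.025. A three-arm ANCOVA (26 df) at 0.025 detects 1.38, 1.26 or 1.04 SD if the correlation of the outcome with baseline is 0.3, 0.5 or 0.7 (assumed).

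**7. Early leavers under the proposed value.** Days 2 to 10 centre on day 6. A patient leaving after day 6 has days 2 to 6, centred on day 4, a shift of 2 days. Leaving after day 7 gives a centre of 4.5, a shift of 1.5 days. Suppose a share of the exosome arm leaves early, nobody in placebo does, and SpO2 rises linearly. The exosome mean is then understated by share × slope × shift:

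- smallest: 0.3 × 0.2 × 1.5 = 0.09 points
- largest: 0.5 × 0.5 × 2 = 0.50 points

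The shares, leaving days and slopes are assumptions.

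**The case against.** This is a Phase 1/2 trial with 10 patients per arm and no stated confirmatory claim. SpO2 is not labelled primary, and the timing points away from it: "The primary outcomes will be assessed at discharge of the clinic and 1 month after", whereas SpO2 is read only on inhalation days. Each daily t-test is valid at its own level. The parenthesis after the box-plot wording supports a display reading, and a specific row would ordinarily govern general text.

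Much of this stands. It confines the point to one efficacy outcome and makes the box-plot wording secondary. It does not remove the main gap: the analysed value is still undefined, and the plan does not call the analysis exploratory.

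Several stronger conclusions are tempting but not supported:

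- **That 27 within-group tests are planned** (days 2 to 10 against day 1, three arms). The general text suggests one start-versus-after test per arm, although it leaves the later day open. Recovery on standard therapy could also change SpO2, so a within-group change is not necessarily a false positive.
- **That ten group-level daily medians per arm are compared.** This needs a second aggregation that the row does not describe.
- **That the contrasts are wholly undefined.** Placebo is named; only separate versus pooled testing is open.

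**Conclusion.** The point holds as a matter to correct, limited to SpO2. Under the assumptions above, claiming an effect from any of ten daily tests carries a false-positive rate per exosome-placebo comparison of about 36% falling to 13% (exchangeable correlation 0.3 to 0.9) or 39% falling to 19% (AR(1) 0.3 to 0.9). Pooling patient-days carries about 32% rising to 54%, or 14% rising to 49%. One value per patient gives about 5% per comparison and about 9% for either arm unadjusted.

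These figures show what follows from each reading. They are not estimates for this trial: alpha and the correlations are assumed, and the plan does not say which reading will be used. A reader might infer that the planned t-test fails its nominal level whatever is done. The documents do not support that, because a single daily test or a per-patient summary would hold it.

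The box-plot wording is a secondary inconsistency: the general text names a display where the SpO2 row names a t-test.

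**What to change.** Replace the SpO2 statistics sentence with:

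> The SpO2 outcome is one value per patient: the mean of that patient's available daily medians from day 2 to day 10. EXO-1 and EXO-2 are each compared with placebo in one three-arm ANCOVA adjusted for the reading before the first inhalation on day 1, at two-sided 0.025 each. Individual daily medians and within-group changes are descriptive. The number of days with readings is listed by arm.

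In the paragraph under the table and in *Demographics and Baseline Characteristics*, state that box-plots are for display only, and replace the single main group with each of the two main groups.

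Costs:

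- No new readings are needed.
- The 0.025 split raises the detectable difference from 1.32 to 1.48 SD before adjustment; adjusting for baseline recovers some or all of that.
- *EXPECTED RESULTS* anticipates shorter stays. If more exosome patients leave early while SpO2 is rising, averaging available days understates the exosome arm, by about 0.09 to 0.50 points under the assumptions in the working. The listing of days with readings lets a reader judge this.
- *Study Design* gives the enrollment of 30 as actual. The change should be dated, made before unblinding if that is still possible, and otherwise labelled post hoc.
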